6.1. Screening

Screening will take place within a 3-week window (Days -21 to -2) before dosing. Informed consent will be obtained from the patient/guardian prior to performing any of the screening assessments. For information regarding re-screening, see Section [4.2.4](#).

The following activities and/or assessments will be performed at/during screening:

- Informed consent (for parent/legal guardian/patient) and depending on the age of the patient, an assent form may also be signed by the patient.
- Inclusion/exclusion criteria.
- Record demographic information (date of birth/age, sex, ethnicity, and race).
- Medical and surgical history, including medication history.
- AE monitoring.
- Concomitant medication monitoring.
- Physical examination, including height, weight, and BMI (derived).
- Pregnancy test based on local practice (for post-menarchal females).
- Patients of childbearing potential (post-menarche) who are sexually active must agree to use an effective contraception method, per local practice, for the duration of the study.
- Blood samples for:
 - Clinical laboratory tests (hematology and serum chemistry) if not performed within 2 weeks prior to screening (refer to Section [9.6](#)).
 - Coagulation (PT, INR, and aPTT).
 - Serology (human immunodeficiency virus [HIV] and hepatitis B and C testing) if not performed within 2 weeks prior to screening.
 - PD blood samples for Cohorts 4 and 5.

- Urine sample for:
 - Urine drug screen for the presence of the following controlled substances: opiates, benzodiazepines, amphetamines, cannabinoids, cocaine, barbiturates, phencyclidine, cotinine levels (non-exclusionary), and alcohol will be performed on patients 12 years of age and older, for newborns, and for patients who are being breastfed.
 - Urine sample for dipstick analysis. Microscopic analysis may be required if dipstick is positive for blood, RBC, or WBC.
- Vital signs including blood pressure, pulse rate, and body temperature after resting at least 5 minutes in a sitting or supine position. (Note: the appropriate cuff size based on arm circumference will be used).

6.2. Randomization

This is not a randomized study. In each age group, patients will be assigned to a particular treatment in a manner that allows for an even distribution of ages across doses (this decision will be made in consultation with clinical study lead).

6.3. Treatment Period

6.3.1. Check-in and Treatment

The following procedures apply to check-in and treatment, as appropriate.

Patients will be asked to fast for at least 4 hours before dosing and for an additional 2 hours after dosing. If this is not feasible because of the patient's age or other needs, (unflavored) milk, or an equivalent substitute liquid (but not fruit juices), will be allowed until 1 hour before dosing and starting at 1 hour postdose. During this period, the total volume of liquids should not exceed 240 mL, excluding the volume of water utilized for dosing.

6.3.2. Check-in (Day -1/1 Predose)

Check-in is scheduled for Day -1; however, check-in may also occur on Day 1 prior to dosing at the clinic's discretion. Patients may be confined from time of check-in until after the last assessment is made on Day 2 (or Day 3 for patients enrolled prior to Version 5.0 of the protocol); however, overnight stays are not required.

The following activities and/or assessments will be performed at/during check-in:

- Reassessment of eligibility.
- Medical and surgical history, including medication history.
- Physical examination, including height, weight, and BMI (derived).
- Pregnancy test based on local practice (for post-menarchal females).

- Urine sample for:
 - Urine drug screen for the presence of the following controlled substances: opiates, benzodiazepines, amphetamines, cannabinoids, cocaine, barbiturates, phencyclidine, cotinine levels (non-exclusionary), and alcohol will be performed on patients 12 years of age and older, for newborns, and for patients who are being breastfed.
 - Urine sample for dipstick analysis. Microscopic analysis may be required if dipstick is positive for blood, RBC, or WBC.
- Vital signs including blood pressure, pulse rate, and body temperature after resting at least 5 minutes in a sitting or supine position. (Note: the appropriate cuff size based on arm circumference will be used.)
- AE monitoring.
- Concomitant medication monitoring.

6.3.3. Treatment Period (Days 1 to 3)

6.3.3.1. Day 1

On Day 1, the following procedures will be performed after the patient has fasted for at least 4 hours (patients will continue to fast until 2 hours postdose). Patients who have not fasted must return on a subsequent day for Day 1 treatment. Any procedure occurring after hour 8 on Day 1 may be performed using a home healthcare service, depending on the availability of the service in the patient's country:

- **All Cohorts:**
 - Edoxaban administration.
 - Assessment of palatability for patients or guardians of patients receiving the edoxaban granule for oral suspension formulation (including bitterness, sweetness, overall taste, and aroma) using 100 mm VAS.
 - AE monitoring.
 - Concomitant medication monitoring.
- **Cohort 1:**
 - Vital signs (including, blood pressure, pulse rate, and body temperature) will be taken before dose administration and within the following windows: 0.25 to 1 hour, 1.5 to 3 hours, and 8.5 to 14 hours postdose. All vital sign assessments will be performed before the scheduled blood sampling for edoxaban and after at least a 5-minute rest in a sitting or supine position. The position in which the vital signs are taken (i.e., sitting or supine) will be recorded in the CRF.

- Serial PK blood samples will be collected after edoxaban administration using a window approach at 0.25 to 1 hour, 1.5 to 3 hours, 3.5 to 6 hours, 6.5 to 8 hours, and 8.5 to 14 hours postdose.
- Serial PD blood samples for estimation of biomarkers of coagulation (aPTT, PT, and anti-FXa) will be collected at predose and immediately after simultaneously scheduled PK sample collections at 0.25 to 1 hour, 1.5 to 3 hours, 3.5 to 6 hours, and 6.5 to 8 hours.
- **Cohorts 2 and 3:**
 - Vital signs (including, blood pressure, pulse rate, and body temperature) will be taken before dose administration and within the following windows: 0.25 to 1 hour, 1.5 to 3 hours, and 9 to 14 hours postdose. All vital sign assessments will be performed before the scheduled blood sampling for edoxaban and after at least a 5-minute rest in a sitting or supine position. The position in which the vital signs are taken (i.e., sitting or supine) will be recorded in the CRF.
 - Serial PK blood samples will be collected after edoxaban administration using a window approach at 0.25 to 1 hour, 1.5 to 3 hours, 4 to 8 hours, and 9 to 14 hours postdose.
 - Serial PD blood samples for estimation of biomarkers of coagulation (aPTT, PT, and anti-FXa) will be collected at predose and immediately after simultaneously scheduled PK sample collections at 0.25 to 1 hour, 1.5 to 3 hours, 4 to 8 hours, and 9 to 14 hours postdose.
- **Cohort 4:**
 - Vital signs (including, blood pressure, pulse rate, and body temperature) will be taken before dose administration and within the following windows: 0.5 to 2 hours, 3 to 8 hours, and 9 to 14 hours postdose. All vital sign assessments will be performed before the scheduled blood sampling for edoxaban and after at least a 5-minute rest in a sitting or supine position. The position in which the vital signs are taken (i.e., sitting or supine) will be recorded in the CRF.
 - Serial PK blood samples will be collected after edoxaban administration using a window approach at 0.5 to 2 hours, 3 to 8 hours, and 9 to 14 hours postdose.
 - PD blood samples for estimation of biomarkers of coagulation (aPTT, PT, and anti-FXa) will be collected immediately after simultaneously scheduled PK sample collection at 0.5 to 2 hours postdose.

- **Cohort 5:**

- Vital signs (including, blood pressure, pulse rate, and body temperature) will be taken before dose administration and within the following windows: 0.5 to 2 hours, 3 to 8 hours, and 9 to 14 hours postdose. All vital sign assessments will be performed before the scheduled blood sampling for edoxaban and after at least a 5-minute rest in a sitting or supine position. The position in which the vital signs are taken (i.e., sitting or supine) will be recorded in the CRF. Note: Patients will receive either 2 or 3 of these vital signs recordings depending on which PK blood sample timepoints they are assigned.
- PK blood samples will be collected after edoxaban administration at a total of 3 of the 4 possible timepoints postdose: 0.5 to 2 hours (mandatory), 3 to 8 hours, 9 to 14 hours, and 24 to 36 hours (on Day 2). The timepoints will be assigned by the Sponsor once the subject is approved to be randomized.
- PD blood samples for estimation of biomarkers of coagulation (aPTT, PT, and anti-FXa) will be collected immediately after simultaneously scheduled PK sample collection at 0.5 to 2 hours postdose.

Exact dates and times of dosing and sample collection will be recorded in the patients' CRFs and used for analyses. At time points when PK, and PD blood samplings occur at the same time, the PK blood samples will be collected first and then PD blood samples will be collected. An overnight stay on Day 1 is not mandatory.

6.3.3.2. Day 2

On Day 2, the following procedures will be performed:

- **All Cohorts:**

- AE monitoring.
- Concomitant medication monitoring.

- **Cohort 1, 2, and 3:**

- PK blood samples will be collected using a window approach at 24 to 36 hours postdose.
- PD blood samples for estimation of biomarkers of coagulation (aPTT, PT, and anti-FXa) immediately after collection of the simultaneously scheduled PK samples at 24 to 36 hours postdose.

- **Cohort 4:**

- PK blood samples will be collected using a window approach at 24 to 36 hours postdose.

- **Cohort 5:**

- Note: For this cohort, only 3 of 4 possible PK timepoints will provide a blood specimen. For patients who provided only 2 PK blood samples on Day 1, a 3rd PK

blood sample will be collected at 24 to 36 hours. No PK blood samples will be collected for patients who provided 3 PK blood samples on Day 1.

Note: the overnight stay on Day 1 is not required; however, the above procedures will occur on Day 2. Some patients may be given the option to have a home healthcare service conduct the Day 2 procedures in the patient's home, depending on the availability of the service in the patient's country. Exact dates and times of dosing and sample collection will be recorded in the patients' CRFs and used for analyses. At time points when PK and PD blood samplings occur at the same time, the PK blood samples will be collected first and then PD blood samples will be collected.

6.3.3.3. Day 3

On Day 3, the following procedures will be performed:

- **PK blood samples for Cohort 1:** will be collected using a window approach at 48 to 54 hours postdose.
- Vital signs (including blood pressure, pulse rate, and body temperature) will be taken 48 to 54 hours postdose. All vital sign assessments will be performed before the scheduled blood sampling for edoxaban and after at least a 5-minute rest in a sitting or supine position. The position in which the vital signs are taken (i.e., sitting or supine) will be recorded in the CRF.
- AE monitoring.
- Concomitant medication monitoring.

Note: the overnight stay on Day 2 is not required; however, the above procedures will occur on Day 3. Some patients may be given the option to have a home healthcare service conduct the Day 3 procedures in the patient's home, depending on the availability of the service in the patient's country. Exact dates and times of dosing and sample collection will be recorded in the patients' CRFs, and used for analyses.

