6. STUDY PROCEDURES

A study visit schedule in tabular format is provided in Appendix [17.7](#). To minimize pain and distress for pediatric patients, the following measures are allowed:

- Use of topical anesthetics
- Use of indwelling cannula

However, heparin should not be used for flushing the cannula.

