17.2. Instructions for Specimen Collection, Storage, and Shipment

17.2.1. Collection, Storage, Handling, and Shipping for Sample Analysis of Plasma Edoxaban (DU-176b) and Metabolites

A blood volume not to exceed the guidelines for pediatrics research for each age cohort⁹ will be taken from specified patients at the times detailed in Section Section 8. Blood loss must not exceed 1% of total blood volume at any time, 3% during 4 weeks. Blood sampling from patients for bioanalytical assessment will use the local methods appropriate for the patient's age to minimize associated blood volume, invasiveness, and pain.

- If 1.0 to 2.0 mL of blood, in accordance to volume guidance described above, can be collected for the specified time points, the following procedures can be applied: blood samples will be collected into pre-chilled 2 mL polyethylene Vacutainer tubes containing lithium heparin as anticoagulant for the preparation of plasma.
- For Cohorts 1 to 3, if less than 1.0 mL of blood can be collected following volume guidance described above, small volume blood collection procedures and devices, deemed age-appropriate locally for collecting lithium heparin plasma can be applied. It is important to ensure that such procedures should not introduce volume bias, i.e., no pre- or post-addition of any solution to the blood collection tube (which may affect the volume of harvested plasma). Recommended devices, and collection procedures, are described in lab manual.

The tube containing blood for plasma preparation will be gently inverted multiple times (≥ 8) to ensure thorough mixing of anticoagulant (lithium heparin) and blood, then placed in a cool box containing ice/water mixture. The samples should be centrifuged within 45 minutes of collection, at approximately 1,500 g for approximately 10 minutes. Immediately following centrifugation, the separated plasma should be pipetted (be careful not to touch the bottom layer), into sample storage vial(s) following the below suggestion:

- If more than approximately 0.3 mL of plasma is harvested, the plasma will be divided approximately equally into 2 polypropylene cryogenic sample storage vials (designated Aliquot 1 and 2) with screw-cap. The sample storage vial volume should not exceed 2.0 mL. Each storage vial should contain more than 100 μ L of plasma.

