17.2.2. Collection, Storage, Handling, and Shipping of Blood Samples for Pharmacodynamic Analysis

The following assays will be made for PD assessments: PT, aPTT, and anti-FXa.

Blood samples (volumes not to exceed the guidelines for pediatrics research for each age cohort⁹) will be collected in sodium citrated blood collection tubes from specified patients at the times detailed in Section 8. Blood loss must not exceed 1% of total blood volume at any time, 3% during 4 weeks. Blood sampling from patients for PD assessment will use the local methods appropriate for the patient's age to minimize associated blood volume, invasiveness, and pain.

For any blood draw, an adequate volume of waste will need to be drawn to clear all tubing of tissue debris or possible contaminants (i.e., heparin) as this may impact analyses. All waste may be returned to the patient per local hospital practices. Please refer to the Laboratory Manual for additional details.

Immediately after the collection, the samples will be mixed by gentle inversion 8 or more times and subsequently within 30 minutes of collection centrifuged at $1,500 \times g$ for 15 minutes. Samples will then be kept on ice, and the resulting platelet poor plasma (being careful not to pipette or disturb cell layer) will then be divided into 3 aliquots (if possible) and transferred to clean screw-topped suitably labeled transfer tubes (cryo vials) as follows:

Aliquots 1 and 2: approximately 0.35 mL per tube

Aliquot 3: Remainder of the plasma sample into the third tube

Note – the volumes and the aliquoting scheme might need to be adjusted for each age cohort.

Aliquot 1 should be shipped first. After receiving confirmation of receipt, Aliquot 2 and 3 should be shipped. All aliquots should be stored at or below -70°C until transferred to Medpace for analysis. Samples should be stored within 60 minutes of collection. Aliquot 1 will be stored in 1 freezer, and Aliquots 2 and 3 will be stored in a different freezer.

All samples must be packed in sufficient dry ice to last 3 days and will be shipped on a Monday, Tuesday, or Wednesday to ensure weekday overnight delivery.

Samples in North America will be shipped to:

PPD

Sample Management

Medpace Reference Laboratories USA

[name]

[name]

PPD

Samples outside North America will be shipped to:

Medpace Reference Laboratories, Belgium

[name]

[name]

PPD

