| Study Hour → | Screening | Check-in ² | Predose | 0.25-1 hour postdose | 1.5-3 hours postdose | 3.5-6 hours postdose | 6.5-8 hours postdose | 8.5-14 hours postdose | 24-36 hours postdose ³ | 48-54 hours postdose | Follow-up ³ |
| Blood sampling for PK ⁴ | | | | X | X | X | X | X | X | X | |
| Blood sampling for PD ⁵ | | | X | X | X | X | X | | X | | |
| Vital signs | X | X | X | X | X | | | X | | X | X |

PD = pharmacodynamic; PK = pharmacokinetic.

1. The overnight stay on Day 1 or Day 2 is not mandatory. The patient may leave the clinic on Day 1 following the completion of all study procedures and return to the clinic on Day 2 for the completion of Day 2 procedures (or Day 3 for patients enrolled prior to Version 5.0 of the protocol). Any procedure occurring after hour 8 on Day 1 may be performed using a home healthcare service, depending on the availability of the service in the patient's country.
2. Check-in may occur on Day -1 or 1, depending on the site.
3. Some patients may be given the option to have a home healthcare service conduct the procedures for this visit in the patient's home, depending on the availability of the service in the patient's country.
4. Sampling scheme may be adjusted for various age cohorts based on emerging PK and safety data. The patient will check-out after the last PK sample has been collected on Day 3.
5. To be concurrent with PK sampling, after PK sampling based on age cohort.

Table 17.3: Pharmacokinetic and Pharmacodynamic Blood Sampling Schedule for Cohorts 2 and 3

| Study Day → | Days -21 to -2 | Day -1/1 predose | | Day 1 ¹ | | | | Day 2 ¹ | Within 10 days after dosing |
|------------------------------------|----------------|-----------------------|---------|----------------------|----------------------|--------------------|---------------------|-----------------------------------|-----------------------------|
| Study Hour → | Screening | Check-in ² | Predose | 0.25-1 hour postdose | 1.5-3 hours postdose | 4-8 hours postdose | 9-14 hours postdose | 24-36 hours postdose ³ | Follow-up ³ |
| Blood sampling for PK ⁴ | | | | X | X | X | X | X | |
| Blood sampling for PD ⁵ | | | X | X | X | X | X | X | |
| Vital signs | X | X | X | X | X | | X | | X |

PD = pharmacodynamic; PK = pharmacokinetic.

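### After dosing only, the lithium-heparin PK tube is drawn just before the citrate PD tube; drawing citrate first would close a possible heparin carry-over route at little cost

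*Combined protocol and SAP*

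**What the plan says.** **Order of draw.** For both Day 1 and Day 2, Section 6.3.3 states that when the two samplings coincide "the PK blood samples will be collected first and then PD blood samples will be collected". For Cohorts 1 to 3, PD samples "will be collected at predose and immediately after simultaneously scheduled PK sample collections at 0.25 to 1 hour" and at the later shared windows. Footnote 5 of Tables 17.2 to 17.4 agrees: "To be concurrent with PK sampling, after PK sampling based on age cohort".

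**Tubes.** Appendix 17.2.1 has PK blood go into "tubes containing lithium heparin as anticoagulant for the preparation of plasma". Appendix 17.2.2 says that PD blood "will be collected in sodium citrated blood collection tubes from specified patients".

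**Baseline.** The baseline PD sample is taken predose in Cohorts 1 to 3 and at screening in Cohorts 4 and 5. Tables 17.2 to 17.4 schedule no PK sample at either point.

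**Safeguards.** Section 6 says that "heparin should not be used for flushing the cannula". Appendix 17.2.2 asks, at any blood draw, for enough waste to clear the tubing of debris or "possible contaminants (i.e., heparin) as this may impact analyses". It allows the waste to be returned to the patient under local practice and refers to a Laboratory Manual for further detail.

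**The concern.** The protocol treats heparin as a threat to the coagulation assays, yet it places a heparin tube directly ahead of the coagulation tube. Heparin prolongs aPTT and adds anti-FXa activity, which is the direction of the drug effect being measured. Because no baseline sample follows a PK tube, carry-over would not cancel in the change from baseline.

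Observed values, change and percent change in PT, aPTT and anti-FXa are the PD endpoints, and Section 11.5.2 uses PK/PD plots to assess age dependence. Three features make an artefact hard to recognise:

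- Anti-FXa had a baseline of 0 in the ex vivo study (Table 1.1, note 1). With a baseline near zero, an added amount passes straight into the change.
- PD volume is smaller in the younger cohorts, so an artefact could look like an age effect.
- Cohorts 4 and 5 have a single postdose PD sample, with no other time point to compare it with.

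**Working it through.** The protocol gives no figure on this point to reproduce. The check has three parts.

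**1. How many PD samples follow a PK tube (Section 8.2.1, Tables 17.2 to 17.4)**

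| Cohorts | Patients | Postdose PD samples each | Of these, after a PK tube | Baseline samples after a PK tube |
|---|---|---|---|---|
| 1 | 12 | 5 | 5 | 0 |
| 2 and 3 | 24 | 5 | 5 | 0 |
| 4 and 5 | 24 | 1 | 1 | 0 |

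Postdose total: 36 × 5 + 24 × 1 = 204, all after a PK tube. Baseline total: 60, none after a PK tube.

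Two limits apply. The order of the other tubes drawn at screening in Cohorts 4 and 5 is not given, so it is established only that no PK tube precedes that baseline. Also, the tube instructions in Appendix 17.2.1 do not specifically cover the 600 µL samples of Cohorts 4 and 5. Lithium heparin for them rests on the general mixing instruction there, which has no cohort limit.

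**2. How carry-over would scale**

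Added heparin (IU per mL of sample) = H × v / V, where H is the heparin concentration in the PK tube, v the carried volume and V the PD sample volume. V is in the protocol: 1.8 mL in Cohorts 1 and 2, 1 mL in Cohorts 3 to 5. H and v are not in the documents. The values below are assumptions: H from 5 to 30 IU/mL, v from 0 to 20 µL.

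| H (IU/mL) | v (µL) | Added, V = 1.8 mL | Added, V = 1 mL |
|---|---|---|---|
| any | 0 | 0 | 0 |
| 5 | 1 | 0.005/1.8 = 0.003 | 0.005 |
| 15 | 5 | 0.075/1.8 = 0.042 | 0.075 |
| 30 | 20 | 0.600/1.8 = 0.333 | 0.600 |

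The range is 0 to 0.33 IU/mL in the larger samples and 0 to 0.60 IU/mL in the smaller. Only the ratio, 1.8/1 = 1.8, does not depend on H and v, and it needs both to be equal across cohorts. Expressing the result per mL of plasma would multiply both columns by the same factor at a common plasma fraction.

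A fixed increment would weigh most where drug effect is lowest. In adults at steady state on 60 mg, Section 1.1.1.5 gives a trough of 15.5 ng/mL against a peak of 303 ng/mL (15.5/303 = 5%). The nearest counterpart here is the 24 to 36 hour sample in Cohorts 1 to 3.

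**3. Does the waste rule close the gap?**

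The rule applies to any draw and names heparin. It does not say whether the PD tube that immediately follows a PK tube counts as a new draw. If it does, the tubing is cleared between the tubes. If a paired collection is one draw, waste is taken before the PK tube and nothing is required between the two. The text supports either reading, and the Laboratory Manual is not among the documents.

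**The case against.** The strongest reply is that the protocol already deals with heparin. The waste rule stands in the PD instructions, covers every draw and all tubing, and can be read to include the PD step. The cost of a discard is limited because the waste may be returned. This stands: a between-tube discard is unclear, not shown to be absent.

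The route itself is also uncertain. An indwelling cannula is permitted, not required, and collection follows local age-appropriate methods, so the documents do not establish that both tubes are filled through one access. The device for the 600 µL samples is not described, and that is where a given carry-over would weigh most. This stands as well.

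A reader might infer that the PD results are biased upward, or that change from baseline can only be inflated. The documents support neither. The carried volume may be zero. The one-way direction belongs to carry-over alone: Section 4.1.1 admits patients on heparin, and in Cohorts 4 and 5 the baseline is taken at screening, when that treatment may be ongoing. A raised baseline would lower the change. That is a separate error in some patients and does not remove the postdose-only route.

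Finally, PD is secondary, the analyses are descriptive and exploratory (Section 11.2), and doses are chosen from PK exposure (Section 11.8). Drawing PK first may protect the primary sample in a difficult draw. These points limit the stakes and qualify the fix, but they do not make the present order preferable for the PD endpoints.

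**Conclusion.** The point holds as a cheap improvement. The order of draw, the two tube additives and the asymmetry (204 of 204 postdose samples against 0 of 60 baselines) are established from the text, with the tube caveat for Cohorts 4 and 5. Any heparin carried over would raise postdose aPTT and anti-FXa only. At equal carried volume and heparin concentration it would weigh 1.8 times more in Cohorts 3 to 5 than in Cohorts 1 and 2.

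The size and frequency of carry-over cannot be derived from the documents. The illustrative range starts at zero and rests wholly on assumed inputs. This is a residual risk to secondary, descriptive endpoints. The edoxaban PK endpoints and the dose decisions based on them are not affected.

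**What to change.** - In the synopsis, Sections 6.3.3.1 and 6.3.3.2, and footnote 5 of Tables 17.2 to 17.4, have the citrate PD tube drawn first and the lithium-heparin PK tube second at each paired time point, with the exact time of each recorded.
- Where PK must stay first to protect the primary sample, say so, and require clearing waste between the PK and PD tubes, returnable as Appendix 17.2.2 already allows. Put the same rule in the Laboratory Manual.
- Record the order of draw for each sample, and flag samples already taken PK-first in the PD listings.
- If the order changes mid-study, consider it when reading age differences. Enrollment runs from oldest to youngest, so a switch could leave older cohorts PK-first and younger ones PD-first. A flag would show this but could not separate order from age.

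**Cost.** Drawing citrate first needs no extra blood or visit. The PK sample moves by about a minute (assumed). The narrowest PK window is 45 minutes (0.25 to 1 hour), and the analysis uses recorded times. The remaining downside is a small risk of losing the PK sample when a difficult draw fails after the PD tube; the second option is there for that case.
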